The overarching goal of this proposal is to a) assess the feasibility and preliminary validity of **home-based delivery of TeleNP** to patients with suspected AD, referred for cognitive assessments in a Neurology Clinic; and b) elucidate whether TeleNP is equivalent to face-to-face evaluation (FF) for diagnostic adjudication of atypical versus typical AD. To accomplish these goals, we will conduct a **pilot clinical trial** of two testing modalities, TeleNP versus FF, for delivery of neuropsychological evaluations. Neurologist-referred patients with typical (i.e., memory-predominant; n=40) and atypical (i.e., complex and/or non-memory predominant; n=40) presentations of *possible* AD will be enrolled in the study. Care partners of participants will also be consented to the study and included in stakeholder surveys/interviews. Using a cross-over design, all participants will undergo evaluations (clinical interview + Core Battery of cognitive tests) in both modalities, approximately 4-6 weeks apart to account for potential practice effects. Although all participants will be referred due to suspected AD, the neuropsychologist will be blinded to the specific diagnosis (i.e. typical versus atypical) from the neurologist. The Core Battery will include measures of memory, executive, visuospatial, and language functions. To further minimize practice effects, alternate assessment forms will be implemented and order of test forms will be counterbalanced. Some tests are not readily adaptable to video-based delivery due to tactile/physical stimuli; as such, we will assess whether a Flexible Assessment (i.e., option to include additional tests, after completion of Core Battery) in the FF modality alters diagnostic conclusions. Finally, in an exploratory aim, we will identify stakeholder perspectives of TeleNP that inform pragmatic implementation of remote neuropsychological evaluations. Our Aims are:

Aim 1: Determine the validity of home-based video administration of neuropsychological tests (TeleNP) for assessing AD. 1a: Are cognitive test results equivalent across TeleNP and FF conditions in patients with suspected AD? 1b. Is this equivalence consistent across referral diagnoses (i.e., Typical vs. Atypical AD)? *This Aim will test the validity of cognitive measures assessed with TeleNP and determine whether the validity of TeleNP differs based on referral diagnosis.*

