Aim 2: Evaluate the impact of home-based TeleNP on the differential diagnosis of typical and atypical AD. 2a. Is the neuropsychologist's diagnosis comparable across TeleNP and FF conditions? 2b. Does flexibility to incorporate additional tests (Flexible Assessment) that are not readily adaptable to video administration alter diagnostic conclusions? *Given that neuropsychologists' conceptualizations of patient presentations may differ from the referring neurologist, this Aim will appraise whether TeleNP results in the same diagnoses from neuropsychologists compared to FF (gold standard) conditions.*

Aim 3: Appraise the feasibility and acceptability of TeleNP in the evaluation of AD patients. 3a. What is the user experience of TeleNP by patients, care partners, neuropsychologists, and psychometrists? 3b. Are there barriers or unique benefits of TeleNP that may influence future use and scalability in clinical care? *This Aim will utilize mixed methods, including interviews about the user experience and surveys of intervention feasibility and acceptability, to address quantitative and qualitative aspects of TeleNP that may influence the pragmatic implementation of remote assessments in a future, definitive trial.*

II. Background and Significance:

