Face-to-face (FF) Assessment (control condition): The participant will undergo an in-person evaluation with the neuropsychologist and psychometrist at the Clinical & Translational Research Center (CTRC) or in Building 400 at CU-AMC. The standard protocol will be administered, including the interview and Core Battery. After completion of the Core Battery and submission of initial ratings, the supervising neuropsychologists may elect to have additional tests administered by the psychometrist as part of a Flexible Assessment. The Flexible Assessment will include a menu of tests that have physical/tactile stimuli (e.g., Design Fluency; Trail Making Test), all of which are excluded from the Core Battery due to lack of adaptability to video-based administration. Upon receipt of the scores from the Flexible Assessment, the neuropsychologist will complete a second form indicating any alterations to their diagnosis based on new information.

TeleNP Assessment (intervention condition): The participant will undergo a video-based TeleNP assessment using a HIPAA-compliant platform (e.g., Zoom). The participant will be at home using a study-provided tablet, and the neuropsychologist and psychometrist will administer the evaluation from either the CTRC or their CU-AMC office. During the scheduled TeleNP assessment, the standard protocol will be administered (i.e., interview and Core Battery). The psychometrist will assist with tablet collection at no direct cost to the participant (i.e., will provide a paid return box; alternatively, participant may drop off tablet if convenient to them)

Data Collection for Clinical Trial Participants:

Medical records:

--Participants will be asked to allow their past, current and future medical record information, to be placed in our RedCap database. The goal is to collect health information pertinent to cognitive functioning in older adults. Because concurrent medical conditions and treatments may impact the participants' health, it is likely that all pertinent past, current and future medical record information will be considered for inclusion in the RedCap database. This will include: symptom history and diagnostic considerations from the participants' neurology notes; laboratory results; health history (i.e., major medical problems); brain imaging results.

Demographics:

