Aim 2: Equivalence of Neuropsychologist's Diagnosis: *Considering that neuropsychologists' conceptualizations of patient presentations may differ from the referring neurologist, the goal of this Aim is to appraise whether TeleNP results in the same diagnoses from neuropsychologists compared to FF (gold standard) conditions, and determine whether inclusion of flexibility to incorporate additional tests (Flexible Assessment) that are not readily adaptable to video administration alters diagnostic considerations.* Neuropsychologist-determined diagnosis (i.e., typical AD, atypical/complex AD, not AD) and severity (i.e., subjective concerns; MCI; dementia) will be assessed immediately after the standard protocol via a REDCap survey. To clarify whether the Flexible Assessment alters the neuropsychologists' conceptualizations, neuropsychologist diagnosis and severity will also be documented after the Flexible Assessment is completed.

Aim 3: Feasibility and Acceptability of TeleNP: *This Aim will utilize mixed methods, including patient, care partner, neuropsychologist, and psychometrist interviews about the user experience and surveys of intervention feasibility and acceptability (i.e., modified UTAUT), to address quantitative and qualitative aspects of TeleNP that may influence the pragmatic implementation of remote assessments in a future, definitive trial.*

Qualitative:

- Patients and Care Partners: **A subset of diverse patients (n=20) and any associated care partners** will be invited to participate in semi-structured interviews with the psychometrist within one week of completing both FF and TeleNP conditions. We will sample for diverse perspectives, including participants from both genders and typical vs. atypical AD. These interviews will focus on the participant's user experience, guided by

UTAUT domains and specific attention to home setting and potential care partner involvement.

- Psychometrist and Neuropsychologists: The psychometrist and neuropsychologists will also participate in brief, separate interviews to garner information regarding feasibility, acceptability, and strengths/weaknesses of TeleNP; these interviews will be conducted by [name] on four occasions, with each interview occurring after completion of 20 study visits.

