F. Statistical Analysis Plan:

For **Aim 1**, we will adopt an equivalence testing framework. The null hypothesis is that there is an average difference of at least .5 SD units in the difference in the z-scores, where .5 SD defines a potentially clinically meaningful difference. The alternative hypothesis is that the mean of the

difference in the z-scores is zero. This is the reverse of standard statistical testing. We elected a .5 SD margin as an initial threshold for a clinically meaningful difference; the reason for this decision is that once an individual reaches a level deemed to be clinically significant impairment (e.g., mild impairment = -1.5 SD; moderate impairment =-2.0 SD), a change in .5 SD equates to a categorical difference in their overall severity rating. To conduct our equivalence test, we will compute the difference in the z-score between the FF and TeleNP conditions and compute the mean difference and a 90% confidence interval based on a t-test. This results in an equivalence test with an alpha=0.05. If the entirety of bounds of the 90% confidence interval are between (-.5SD, .5SD), then the two assessments will be considered equivalent. We will repeat this computation stratified by referring diagnosis (typical vs. atypical), and also by sex or race/ethnicity (white vs. non-White).

For **Aim 2**, we will compute a 3x3 table with the rows as TeleNP diagnosis and the columns as FF diagnosis to summarize the results. To assess the equivalence of TeleNP and FF for each condition we will create 3, 2x2 tables. For example, when assessing for differences in typical AD we will collapse over atypical AD and Not AD. Following prior work³⁵, we will compute the difference proportion of typical AD for the TeleNP and FF setting and construct a 90% confidence interval. A difference of proportions greater than 5% will be considered a clinically meaningful difference. If the 90% confidence interval is between (-5%,5%), then the two modalities will be considered equivalent. We will repeat this process for the two other neuropsychologist-determined categories (atypical AD, Not AD). We will conduct the same analyses, stratified by severity. We will assess whether the neuropsychologists' diagnosis is equivalent to the Flexible Assessment by repeating the above analysis using the Flexible vs FF diagnosis (i.e., diagnosis reported prior to initiating Flexible Assessment).

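### Aim 2b asks whether Flexible testing alters the diagnosis, but the verdict rests on a net difference in proportions, in which opposite changes cancel, over an unstated set of patients

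*Combined protocol and SAP*

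**What the plan says.** Section I (Specific Aims) puts Aim 2b as a question about change: "Does flexibility to incorporate additional tests (Flexible Assessment) that are not readily adaptable to video administration alter diagnostic conclusions"? Section IV.B (Assessment Modality Details, face-to-face) makes the extra testing discretionary. Once the Core Battery is done and initial ratings are submitted, "the supervising neuropsychologists may elect to have additional tests administered by the psychometrist as part of a Flexible Assessment". When those scores arrive, "the neuropsychologist will complete a second form indicating any alterations to their diagnosis based on new information". Section IV.C (Aim 2) confirms that "neuropsychologist diagnosis and severity will also be documented after the Flexible Assessment is completed". The design overview in Section I describes the Flexible Assessment as an "option to include additional tests, after completion of Core Battery".

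Section IV.F defines the main Aim 2 analysis for each of three categories (typical AD, atypical AD, not AD): "we will compute the difference proportion of typical AD for the TeleNP and FF setting and construct a 90% confidence interval". The decision rule is: "If the 90% confidence interval is between (-5%,5%), then the two modalities will be considered equivalent". For Aim 2b the SAP prescribes "repeating the above analysis using the Flexible vs FF diagnosis (i.e., diagnosis reported prior to initiating Flexible Assessment"). A 3x3 table is also produced as a summary, but no decision depends on it.

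**The concern.** Whether added tests alter a diagnosis is a question about individual patients: how many had a different diagnosis afterwards? The difference in a category's proportion before and after measures only the net shift in that category's total. One patient moving from typical to atypical and another moving the opposite way give a difference of zero, although two diagnoses changed.

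The second problem is the denominator. The before/after forms suggest that only patients given Flexible tests are compared. The word option also allows an analysis of everyone assessed face-to-face, with untested patients unchanged by definition. The SAP does not choose, and the ±5% rule behaves very differently in the two sets.

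Aim 2b is the plan's own check on whether leaving out tests that cannot readily be given by video matters for diagnosis. A rule that can call more changes equivalent and fewer changes not equivalent does not answer that.

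**Working it through.** **Inputs.** Planned sample 80 (Section IV.A). Three diagnostic categories (IV.C). 90% interval and ±5% margin (IV.F). The documents give no expected change rate, no power for Aim 2 and no number of patients expected to have Flexible tests, so there is no figure of the plan's to reproduce. IV.F refers to prior work for the method but writes out no formula, so two paired intervals are shown.

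**Formulas.** Let b and c be the patients moving into and out of a category, n the number analysed, z = 1.645.

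- Paired Wald: (b - c)/n ± z·√(b + c - (b - c)²/n)/n.
- Tango score: the two values D that solve (b - c - nD)/√(n[2q + D(1 - D)]) = ±z, where q is the maximum-likelihood estimate of the probability of moving out, given D.

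**Step 1. One category, n = 80.** Two Wald examples in full:

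- Two in, none out: 2/80 = 2.5%; SE = √(2 - 4/80)/80 = 1.75%; interval 2.5 ± 2.87, that is -0.37% to 5.37%. Fails.
- Two in, two out: 0%; SE = √4/80 = 2.5%; interval ±4.11%. Passes.

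| In, out | Patients changed | Wald 90% CI (%) | Tango 90% CI (%) |
|---|---|---|---|
| 0, 0 | 0 | 0 to 0, pass | ±3.27, pass |
| 1, 0 | 1 | -0.79 to 3.29, pass | -2.06 to 5.41, **fail** |
| 1, 1 | 2 | ±2.91, pass | ±4.31, **pass** |
| 2, 0 | 2 | -0.37 to 5.37, **fail** | -0.85 to 7.28, fail |
| 2, 2 | 4 | ±4.11, **pass** | ±5.15, fail |
| 3, 3 | 6 | ±5.04, fail | ±5.87, fail |

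Under either method a result with more changes passes while one with fewer fails.

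**Step 2. All three categories together, n = 80.** All patterns with 0 to 4 patients in each of the six category-to-category flows were enumerated, and all three categories had to pass. Under Wald, up to 6 changes pass (2 per step of a cycle through the categories) and as few as 2 fail. Under Tango, up to 3 pass (1 per step) and as few as 1 fails.

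**Step 3. Same true change rate, different direction.** Suppose 5% of patients truly change between two categories (n = 80). The chance that one of those categories passes is the trinomial probability summed over the passing (b, c) pairs.

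- Balanced, 2.5% each way, Wald: 0.0165 for (0,0), 2 × 0.0348 for (1,0) and (0,1), 0.0723 for (1,1), 2 × 0.0742 for (2,1) and (1,2), 0.0752 for (2,2). Sum 0.382.
- All one way, Wald: 0.95^80 + 80 × 0.05 × 0.95^79 = 0.0165 + 0.0695 = 0.086.
- Under Tango the figures are 0.089 and 0.017.

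**Step 4. Tested patients only.** Smallest number tested at which each pattern passes:

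| In, out | Wald | Tango |
|---|---|---|
| 0, 0 | any n (zero-width interval) | 52 |
| 1, 1 | 47 | 69 |
| 1, 0 | 53 | 87 (more than the 80 planned) |
| 2, 2 | 66 | 83 (more than the 80 planned) |
| 2, 0 | 86 (more than the 80 planned) | 118 (more than the 80 planned) |

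So a single change passes under Wald with 80 analysed (-0.79% to 3.29%) and fails with 40 (-1.56% to 6.56%). The unstated analysis set can decide the verdict.

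**The case against.** The strongest reply has five parts.

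- **Cancellation is bounded.** Only the point estimate cancels; discordant pairs widen the interval. At n = 80 no more than 6 changes (7.5%) can pass under Wald, or 3 under Tango. With a true, balanced 10% change rate between two categories, the chance that one of them passes is only 4.5% (Wald) or 0.4% (Tango). This stands: the rule is unlikely to hide frequent changes. It does not restore the ordering at the low change counts where the verdict is decided.
- **The text favours tested patients only.** Both the second form and the SAP's wording presuppose that Flexible testing took place. That is the better reading. The reversal then needs at least 47 tested under Wald or 69 under Tango. Below those numbers the fault is different: no pattern containing any change can pass, and below 52 Tango fails even with none. The verdict is uninformative on that reading too.
- **The interval method may be fixed in the cited prior work.** It may. Individual examples depend on it, but the reversal appears under Wald, Tango and the Bonett-Price adjusted interval. An unpaired interval would not show it for category prevalences of 10% to 50%, because its half-width at n = 80 is 7.8 to 13.0 points and it fails even with no changes. It is also unsuitable for two ratings of the same patient.
- **The 3x3 table shows every change.** True, and it limits the harm, but the table carries no decision.
- **A one-way shift is systematic and deserves stricter treatment.** Reasonable, and a case for still showing direction. It does not justify making net shift the sole criterion when the question is whether diagnoses change.

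**Conclusion.** The concern holds and should be fixed. Aim 2b's equivalence verdict measures net movement between categories, not alteration of diagnoses. With 80 analysed, two changes can fail while six pass (Wald), or one can fail while three pass (Tango). With tested patients only and fewer than about 50 of them, the rule either passes only at zero changes or cannot pass at all.

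The mismatch between question and measure is certain from the text. The sizes rest on three assumptions: all 80 planned patients have a face-to-face visit, the interval is a paired one, and the number tested is unknown. To show how much that last number matters, 4 changed diagnoses would be 5% of 80, 10% of 40 or 20% of 20.

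This is a pilot, Aim 2b is one sub-question of Aim 2, and the changes remain visible in the descriptive table. The fault lies in the verdict; no data are lost.

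**What to change.** In Section IV.F, replace the ±5% net-difference rule for Aim 2b with estimation of change:

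1. Report how many of the patients assessed face-to-face had Flexible tests elected.
2. Among those tested, report the proportion whose diagnosis changed in any direction, with an exact (Clopper-Pearson) 95% interval. Do the same separately for severity.
3. Report the any-change proportion over all patients assessed face-to-face, counting untested patients as unchanged. This describes the effect of having the option available.
4. Show the before/after 3x3 table, which keeps the direction of change. The net difference can stay as a descriptive figure without a margin.
5. State both denominators in the SAP.

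The new measure ranks results by the number of changes: with 80 analysed, 2 changed is 2.5% (0.3% to 8.7%), 4 is 5.0% (1.4% to 12.3%) and 6 is 7.5% (2.8% to 15.6%).

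The cost is SAP wording only, since diagnosis and severity before and after Flexible testing are already recorded. There are three downsides. Aim 2b loses its yes/no verdict. The tested-only proportion applies only to patients whom the neuropsychologist chose to test further. The interval is wide if few are tested: with zero changes the exact upper limit is 16.8% for 20 tested, 8.8% for 40 and 4.5% for 80.

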--Participants' age, birthdate, sex, gender, education level (Years), race/ethnicity, prior occupation, etc. will be obtained. Participant's contact information and address will also be obtained to facilitate scheduling baseline and follow-up appointments.

Interview:

--Participant's symptom history will be documented on a standard data collection sheet during the interview portion.

Neuropsychological Testing, Core Battery (May not be given in its entirety):

- Cognitive/Mood Surveys:
 - Geriatric Depression Scale
- Cognitive Assessments:
 - Global:
 - MoCA, with alternate forms
 - Memory:
 - CVLT-II, with alternate forms
 - Benson Figure Recall / RBANS Figure Recall
 - Speed/Executive Functions:
 - Oral Trail Making Test
 - Oral Symbol Digit Modality
 - Digit Span, with alternate forms
 - Verbal Fluency, with alternate forms (FAS; BHR)
 - Color Word Inhibition
 - Language:
 - Sentence Repetition
 - Boston Naming Test-15 item, with alternate forms
 - Verbal Agility
 - WRAT Reading
 - Abbreviated Peabody Picture Vocabulary Test
 - Syntactic Comprehension
 - Visuospatial and Posterior Cortical Function
 - Judgment of Line Orientation (Short Form)
 - Benson Figure Copy / RBANS Figure Copy
 - Calculation Screen

Neuropsychological Testing, Flexible Assessment:

- Cognitive Assessments in addition to Core Battery (May not be administered in its entirety):
 - Grooved Pegboard
 - Clock Drawing Test
 - Rey-Osterrieth Complex Figure
 - BVMT
 - Navon Figures
 - Face Perception/Affect Naming
 - VOSP Number Localization
 - Design Fluency
 - Written Trail Making Test A & B

Surveys:

- 4-item measures of acceptability and feasibility
- 19-item modified UTAUT after TeleNP portion

Cognitive Composites, Neuropsychologist Diagnosis, and Interviews: See Outcome Measures Below

Data Collection for Care Partner Participants:

Demographics:

--Care partner's age, birthdate, sex, gender, education level (Years), race/ethnicity, prior occupation, etc. will be obtained. Participant's contact information and address will also be obtained to facilitate scheduling baseline and follow-up appointments.

Surveys:

- 4-item measures of acceptability and feasibility
- 19-item modified UTAUT after TeleNP portion

Interviews: See Outcome Measures Below

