Quantitative: To appraise feasibility of TeleNP, we will include measures of enrollment tracking (i.e., enrolled vs. decline), protocol assessment time, tracking of protocol adherence (i.e., completion of Core Battery), and presence of technological difficulties (e.g., termination of assessment due to technological difficulties). **The psychometrist will ask all patients (n=80) and associated care partners (up to n=80)** to complete validated 4-item Acceptability and Feasibility of Intervention Measures^{32, 33} after both conditions, and a 19-item UTAUT questionnaire (adapted to TeleNP) after the TeleNP condition to measure determinants of intention to use.

We will document the fidelity of assessment administration and scoring using a fidelity checklist in a random 20% sample of participants.

Costs and Payments

All costs associated with the implementation and maintenance of the study shall be supported by [name] grants. There is no charge to participants or participants' insurance for participation.

Clinical Trial participants will receive \$25 to compensate for their time after both visits are completed. Care partners will not be compensated.

C. Description, Risks and Justification of Procedures and Data Collection Tools:

Description of Risks:

Potential risks to participants, by intervention, including physical, psychological, social, cultural, financial, and legal risks: For both conditions, there are no expected physical or legal risks. Participants will be advised that the clinical trial is voluntary, and that they may obtain a clinical neuropsychological evaluation in lieu of the research study as part of standard of care.

Risks associated with neuropsychological assessments:

- Both conditions (FF [control] and TeleNP [intervention]): The potential risks associated with participation in the study are minimal and include the risk of anxiety and/or fatigue, boredom or frustration during the completion of the neuropsychological testing sessions. An additional potential risk is loss of confidentiality, which could lead to potential social or cultural risks, if personal sensitive information is shared outside of the intervention.
- TeleNP: For the TeleNP condition, there are no expected physical, social, cultural, financial or legal risks. One potential risk is loss of privacy and/or confidentiality, as described below. We will employ video-based assessments for the TeleNP section, using HIPAA-compliant platforms.

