For Aim 3, Feasibility and Acceptability of Intervention Measures and the UTAUT will be analyzed descriptively with means and interquartile ranges. Analysis of qualitative data will be a continuous process beginning with initial interviews and continuing throughout the data generation period. All interviews will be audio-recorded and transcribed verbatim. Directed by [name], rapid qualitative analysis³⁶ will be used to understand multiple user perspectives on feasibility, acceptability, and other potential factors affecting use, including home context, of TeleNP compared to FF. At least 2 team members will analyze transcripts.³⁷ All data will be entered into ATLAS.ti v8.0 (GmbH, Berlin) for data management. Transcripts will be analyzed to develop the major themes or concepts reported by interviewees. Using the quantitative and qualitative data, we will conduct sequential mixed methods analyses using data from Aim 3.³⁸ The synthesis stage of data analysis involves triangulating the findings from interviews and quantitative data related to feasibility (i.e., assessment time, protocol adherence, technical issues, etc.), acceptability ratings, availability of a care partner, etc. We will interpret and summarize feasibility and acceptability for each modality from the different user perspective

G. Summarize Knowledge to be Gained:

Appraisal of the feasibility and validity of TeleNP in patients with complex AD presentations will provide a critical platform for the future development of a pragmatic, multi-site trial. Validation of TeleNP in a real-world setting will further increase access to neuropsychological evaluations and reduce patient burden. Specific knowledge to be gained includes:

- Comparison of two testing modalities for neuropsychology: telehealth and standard, face-to-face assessment
- Comparison of diagnostic adjudication for these two neuropsychology modalities
- Test- and interview-specific differences in feasibility and validity in these two modalities

- Qualitative information regarding feasibility, participant experience and acceptability, care partner experience and acceptability, and psychometrist & neuropsychologist experience.
- Greater understanding of technological concerns that may arise in telehealth
- Preliminary understanding of potential benefits of telehealth, both qualitatively and quantitatively

H. References:

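### Aim 3 summarises the acceptability and feasibility ratings separately by modality, so the TeleNP-versus-FF contrast has no stated precision; a within-person difference with a 95% CI would supply it (minor)

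*Combined protocol and SAP*

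**What the plan says.** In the Outcome Measure(s) section, under Aim 3 (Quantitative), all 80 patients and up to 80 care partners are asked for the 4-item acceptability and feasibility measures "after both conditions, and a 19-item UTAUT questionnaire (adapted to TeleNP) after the TeleNP condition". The UTAUT therefore relates to TeleNP alone, and the 4-item measures are the only rating scale that could set the two modalities side by side.

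Section F (Statistical Analysis Plan) gives the whole quantitative analysis of these scales in one sentence: "Feasibility and Acceptability of Intervention Measures and the UTAUT will be analyzed descriptively with means and interquartile ranges". It ends the Aim 3 paragraph with "We will interpret and summarize feasibility and acceptability for each modality from the different user perspective". It mentions no within-person difference, interval or handling of visit order. For Aim 1, the same section computes each patient's FF-TeleNP difference and puts a 90% confidence interval on its mean.

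Section G lists among the knowledge to be gained a comparison of the two modalities, differences between them in feasibility, and an understanding of the benefits of telehealth that is partly quantitative.

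Under Assessment Modality Details, only the FF visit can grow beyond the interview and Core Battery: the neuropsychologist "may elect to have additional tests administered by the psychometrist as part of a Flexible Assessment". The documents do not say whether the FF rating is taken before or after those tests, or whether the tracked assessment time includes them.

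**The concern.** The cross-over yields two ratings from each person, and the natural summary is the change within that person. Reporting each modality separately discards the pairing. A reader can subtract one mean from the other but cannot tell how uncertain the result is, because that depends on the within-person correlation, which separate means and interquartile ranges do not reveal.

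Missing ratings add a second problem. The enrolment figures allow for withdrawals, and the feasibility measures include assessments ended by technical failure. Someone with only one rating enters one mean and not the other, so the difference between means partly reflects who is missing.

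At stake is how useful the acceptability result will be for planning the later definitive trial. No equivalence decision or safety conclusion depends on it.

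**Working it through.** **Plan's own figure.** None. The documents give no SD, correlation, margin or precision target for Aim 3, so there is nothing to reproduce.

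**Inputs.** From the documents: 80 patients, up to 80 care partners, cross-over with randomised order. Assumed: within-person correlation r of 0.3, 0.5 or 0.7; equal SDs in the two modalities; n=64 to stand for 20% without both ratings; n=40 to stand for half of the patients having a care partner who rates both visits. Results are in units of the rating SD, because the documents do not give the response scale.

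**Step 1: what separate means give.** If the same people rate both modalities, mean(TeleNP) − mean(FF) = mean(TeleNP − FF). The point contrast is available.

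**Step 2: what they do not give.** The SD of the difference is √(S_T² + S_F² − 2·r·S_T·S_F), which becomes SD × √(2(1−r)) when the two SDs are equal. Since r is not reported, the interval cannot be rebuilt from the planned summaries.

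**Step 3: precision.**
- Paired 95% half-width = t(0.975, n−1) × √(2(1−r)/n).
- Pairing ignored = t(0.975, 2n−2) × √(2/n).

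At n=80:
- r=0.3: 1.990 × √(1.4/80) = 0.263
- r=0.5: 1.990 × √(1.0/80) = 0.223
- r=0.7: 1.990 × √(0.6/80) = 0.172
- pairing ignored: 1.975 × √(2/80) = 0.312

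| Pairs | r=0.3 | r=0.5 | r=0.7 | Pairing ignored |
|---|---|---|---|---|
| 80 | 0.26 | 0.22 | 0.17 | 0.31 |
| 64 | 0.30 | 0.25 | 0.19 | 0.35 |
| 40 | 0.38 | 0.32 | 0.25 | 0.45 |

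**Step 4: missing ratings.** Suppose 80 people rate FF and 64 of them also rate TeleNP. The difference between the two means then equals the paired difference in the 64, plus (1 − 64/80) = 0.20 times the gap in mean FF rating between the 64 and the other 16. The extra term is zero only if those 16 rate FF like the rest.

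**Step 5: the Flexible Assessment.** If FF is rated after it, the shift in the FF mean is the share of visits that include it times its average effect on the rating. Neither figure is in the documents. With assumed shares of 25% to 75% and assumed effects of 0.1 to 0.5 SD, the shift runs from 0.25 × 0.1 = 0.025 SD to 0.75 × 0.5 = 0.375 SD. That spans negligible to larger than the half-widths at n=80, so no size can be claimed.

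**The case against.** Aim 3 is labelled exploratory. It asks about the user experience of TeleNP and its barriers and benefits, and it states no hypothesis that TeleNP is as acceptable as FF. Aims 1 and 2 do pose equivalence questions, and they have margins and intervals. The phrase "including home context, of TeleNP compared to FF" belongs to the qualitative analysis of interviews, not to the ratings. A summary for each modality is what Section F promises, and separate means deliver it. The paired records will remain in the database. All of this stands: the descriptive analysis is a legitimate choice, and the interval is an improvement to it. It does not remove the case for an interval, because Section G does expect the modalities to be compared, partly quantitatively, and the patient interviews cover a subset of 20.

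The timing of the ratings is also open to another reading: one occasion once both visits are done. The commitment to summarise each modality makes a rating after each visit the likelier meaning, but the text does not settle it.

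A reader might infer that the FF rating follows a longer visit and that the contrast is therefore biased towards TeleNP, especially in complex patients. The documents do not support this. They do not place the rating after the Flexible Assessment, say how often that assessment is used, show that extra tests lower ratings, or give a rule for who receives them; the neuropsychologists are blinded to the typical or atypical referral. The extra tests are also part of the FF modality as designed, so a longer FF visit may be a real feature of FF. Rating before or after them is a choice of what to estimate.

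**Conclusion.** The point holds as a minor one. The planned summaries leave the TeleNP-versus-FF contrast in acceptability and feasibility without stated precision, and they mix different people when ratings are missing. At n=80 a paired interval would be about ±0.17 to ±0.26 SD, against ±0.31 SD with the pairing ignored. This rests on assumed correlations of 0.7 to 0.3, equal SDs, complete pairs, and the reading that each modality is rated.

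A reader might go further and conclude that Aim 3 cannot say how TeleNP compares with FF. That is too strong: with complete data the point contrast follows directly from the two means. The Flexible Assessment is a matter for clarification. A bias is possible, but its size cannot be derived from the documents.

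**What to change.** In Section F, Aim 3, add the mean within-person TeleNP-minus-FF difference in each 4-item measure with a 95% CI. Report it separately for patients and care partners, and average the order-specific means with equal weight so that a visit-order effect does not enter. Label it a descriptive estimate, with no test and no margin, and give the number of complete pairs.

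In the Outcome Measure(s) section, state that the 4-item measures are completed after each modality, if that is the intention, and whether the FF rating comes before or after any Flexible Assessment. Either is defensible once stated. A rating before it compares like content; a rating after it covers the whole FF visit. Report assessment time for interview plus Core Battery beside total FF time.

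The cost is one extra table and a line on survey timing. No additional data are needed if both ratings are already collected, but the timing has to be settled before collection because it cannot be recovered afterwards.
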